4. To explore the relationships of the psychosocial variables and intervention effectiveness (e.g. meditation, moderation and other associations).

- 5. What are the participating mothers' experiences in the dyadic expressive arts-based intervention group?
- 6. The potential factors and conditions that may affect how and why the EXAT intervention works or does not work for the participating dyads; mothers' perception, acceptability, and real-life application of the non-verbal communication skills that they explored and practiced in the intervention.

Study Design and Methods of Data Collection

Study Design. This proposed study adopts a RCT with *mixed methods design*. To address the research objectives, data collected will be triangulated and interpreted simultaneously to address the research questions. **Appendix A** depicts the CONSORT flow diagram of the present study. Outcome measures will be assessed on four time-points (T_0 : Pre-intervention at baseline; T_1 : Post-intervention; T_2 : 3-month post-intervention and; T_3 : 6-month post-intervention) to assess the immediate and sustained effects of the Dyadic EXAT Group on mother-child relationship and psychosocial wellness. Qualitative interviews will be conducted with a random subsample of 30 parents from the expressive arts intervention at T_1 and T_3 to collect fine-grained, information to explore their overall experience of participation in the intervention and how the experience has shaped their caregiver experience in terms of stress coping and establishing parent-child relationship. Results of the qualitative interviews will be used to enhance the interpretation and understanding of the quantitative findings [33]. Appendix B summarizes the conceptual framework of the proposed study.

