Participants. Participants are mother-child dyads composing of a mother caregiver and a child who is aged 6-12 years (primary school student) and fulfils the diagnostic criteria for *mild* grade to moderate grade ID (based on the age-relevant IQ test assessments administered by a qualified professional). In the judgment of health/school professional staff, the child is capable of responding to assessments and participating in group activities. The dyads are able and willing to give consent for participation in the study (guardian's assent consent will be arranged for the participating children, while written consent will obtained from the adult mothers). Dyads are excluded if: (i) the dyad is currently participating in any other behavioral or pharmacological trial, and/or (ii) either member of the dyads have other contraindications or severe comorbidities that may impair their full participation (e.g. severe physical disabilities).

Recruitment. The recruitment will be facilitated by our collaborative partners in the community (including SEN schools, and community-based units that serve families of children with ID), as well as referral from medical and mental health professionals working in the field of education, paediatric psychiatry, clinical psychology, and social work. The promotion materials will be hosted on the website/social media of the Department of Social Work and Social Administration and Centre on Behavioural Health of The University of Hong Kong. Screening for eligibility will be conducted by the researcher or referral professionals who have attended briefing sessions offered by the research team.

Sample Size: We expected a moderate effect size of 0.5 for the primary outcomes based on a local study [57]. Using power analysis software Gpower 3.1, assuming an attrition rate of 20%, a total sample size of 154 participants (i.e. 77 each arm) will provide 80% statistical power to detect an effect size of 0.5 in the 2-arm RCT with 4 measurement time points at 5% level of significance. For the qualitative data collection, a random subsample of 30 participating mothers will be invited to join individual, in-depth interviews at post-intervention (T₁) and 6-month follow-up (T₂). Based on various guidelines for mixed methods study design, a sample of 25 participants would suffice data saturation. If data saturation is not reached, more participants will be recruited into the study until no more new findings emerge [34].

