In-depth Interviews: 30 participating mothers will be invited to attend two individual, in-depth interveiws at post-intervention (T₁) and 6-month follow-up (T₃) respectively. The first interview focuses on the immediate post-intervention changes percieved by the mothers upon program completion, while the second interview focuses on the sustainability of these changes at 6-month follow-up and explores additional changes that were observed between the follow-up windows. The interviews will be conducted by member of the research team (who are familiar with mixed-methods study design, in-depth interview), assisted by a research assistant, using an interview guide [57]. **Appendix D** shows the sample interview guide and its potential probes.

Data Analysis: Analyses of the outcomes will be performed according to standard intent-to-treat principle to address the effects of crossover and dropout. Missing data for the participants who drop out of the study at follow-up assessments will be handled using the full information maximum likelihood method. This method has been shown to produce unbiased estimates for clinical trials with missing data [58].

[figure not shown]
- 1. Effectiveness of Dyadic EXAT group (Hypothesis 1 3). Descriptive statistics will be used to summarize the socio-demographic characteristics of the participants at all time points. Primary analysis of treatment outcomes will be conducted using mixed-effects regression models. Mixed-effects models analyze the repeated measurements between groups to obtain the time effect, group effect, and group*time effect. The analysis will adopt the intention-to-treat principle to account for the missing data. Missing data for participants' dropout will be handled using full information maximum likelihood method [58]. Effect size of the intervention will be evaluated using Cohen d [59], with 0.2, 0.5, and 0.8 denoting cut-off of small, moderate, and large magnitudes. Demographic and clinical variables will be controlled in the analysis. All statistical tests will be two tailed and statistical significance will be set at 0.05 using Mplus 8.3.

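### EXAT mothers lost before T1 have no interview, and the guide never asks why a mother stopped or missed sessions, so the answer to why EXAT does not work is weaker than it need be

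*Combined protocol and SAP*

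**What the plan says.** The secondary objective includes mothers' experience of the programme (ix) and the factors that affect its outcomes (x). Exploratory question 6 asks "how and why the EXAT intervention works or does not work for the participating dyads", and also about mothers' perception and acceptance of the approach.

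The evidence comes mainly from interviews. Study Design takes a "random subsample of 30 parents from the expressive arts intervention at T_1 and T_3". The In-depth Interviews paragraph sets the content: "The first interview focuses on the immediate post-intervention changes percieved by the mothers upon program completion". The second interview covers whether those changes have lasted and what else has changed by six months.

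On loss of participants, Sample Size states: "assuming an attrition rate of 20%, a total sample size of 154 participants (i.e. 77 each arm) will provide 80% statistical power". The same paragraph gives 25 participants as enough for saturation and allows more to be recruited if saturation is not reached. Data Analysis handles dropout in the outcome assessments by intention to treat and full information maximum likelihood.

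In the guide (Appendix D), item 1 probes acceptability and satisfaction, items 2 to 6 ask about changes since before joining, and item 7 asks for the reasons for change or for lack of change. No item concerns stopping, missed sessions or barriers to attendance.

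**The concern.** A mother who gives up the sessions because they were impractical, unwelcome or unhelpful for her child is an obvious source for the failure half of question 6. The plan sets interviews at T1 and T3 only. A mother who has left the study before T1 has neither contact, and no other interview time is offered. A mother who stopped attending but stayed in the study can be interviewed, but the first interview is framed on finishing the programme and nothing in the guide asks why she stopped.

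The likelihood method for missing questionnaire scores has no counterpart here, because it cannot supply an interview that was never held. Nor does the saturation rule settle the matter: themes can saturate among the mothers who are reached without reasons for stopping ever coming up.

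The themes are to be triangulated with the quantitative results to judge effectiveness. The quantitative analysis covers all randomised dyads. If the interviews miss mothers lost early, the two sources describe somewhat different groups while both appear to speak for the EXAT arm.

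**Working it through.** **1. The plan's own figure.** Inputs from Sample Size and Data Analysis: effect size 0.5, 80% power, two-sided 5%, 1:1 allocation, 20% attrition. A two-sample t-test needs 63.77, rounded up to 64 per arm. Then 64 × 1.20 = 76.8, rounded up to 77 per arm, or 154 in total. The stated figure is reproduced when attrition is added as a multiplier. (Dividing by 0.80 instead gives 64 / 0.80 = 80 per arm, which is a separate matter.) The 20% is therefore a planning allowance for loss from the study, applied to both arms across four time points. It is not a rate of stopping EXAT.

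**2. How many of the 30 could be affected.** The rate of stopping before T1 is not in the documents, so it is varied here as an assumption p. With 77 mothers in the arm and a random 30 drawn from all of them, the expected number is 30 × p.

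| Assumed p | Of 77 EXAT mothers | Expected in a random 30 | Left if none of them is interviewed |
|---|---|---|---|
| 10% | 7.7 | 3 | 27 |
| 20% | 15.4 | 6 | 24 |
| 30% | 23.1 | 9 | 21 |

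The plan's saturation figure of 25 is missed once 30 × (1 − p) falls below 25, that is when p exceeds 5/30 = 16.7%.

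**3. How the 20% relates to p.** If all of the 20% were lost before T1, p would be 20%. If half were lost before T1, that is 77 × 0.20 / 2 = 7.7 mothers, so p = 10%, and about 3 of a random 30 would be affected. The other 7.7 would leave after T1, and on the assumption that they finished the programme they would be completers. Of the 77 − 7.7 = 69.3 mothers still present at T1, a random 30 would include 30 × 7.7 / 69.3 = 3.3 of these later leavers. They could give the first interview but might miss the second.

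**4. What each group can contribute under the text as written.**

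- *Finishes the programme:* both interviews, including the lack-of-change questions.
- *Stops sessions but stays in the study:* can be drawn and interviewed at T1 and T3, but is not asked why she stopped.
- *Leaves the study before T1:* no interview at all.
- *Leaves after T1:* first interview only.

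**The case against.** The strongest reply is that the plan is silent on mothers who stop and does not exclude them. This is right, and it limits the point. Three stronger readings are tempting, and the documents do not support them.

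- **That only completers are interviewed.** The stated frame is a random subsample of the EXAT arm with no completion condition. The sentence about programme completion describes the topic and timing of the first interview, not who may be selected.
- **That question 6 is answered mainly by mothers whom EXAT suited.** Completing is not benefiting. Item 7 asks mothers who report no change for the reasons, and item 1 probes acceptability. Data Analysis also mentions qualitative data from an open-ended questionnaire packet, although nothing says it is collected from mothers who leave.
- **That about 6 of a random 30 would be leavers, against none in practice.** This treats the 20% as EXAT stopping and places all of it before the programme ends. Step 3 of the working shows how the contrast shrinks if half the loss comes later.

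It would also be wrong to put a percentage on any overstatement of acceptability. The documents give no such rates, and the planned analysis is inductive and thematic, so it estimates none.

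Two further replies carry some weight. The participant flow diagram in Appendix A is not visible in the available text and might show the sampling. And no wording can secure an interview with someone who has withdrawn and declines. Neither reply supplies an interview time before T1 in the text, or a guide question on stopping.

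**Conclusion.** The point holds as a limited gap. Interviews are fixed at T1 and T3, so a mother lost before T1 contributes nothing, and the guide asks nobody why she stopped or missed sessions. That weakens the answer to question 6 on failure and acceptability. The text also does not say when the 30 are drawn or how a selected mother who has left is replaced.

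The size is not known from the documents. On an assumed 10% to 30% stopping before T1, about 3 to 9 of a random 30 would be mothers who stopped. None would be asked the reason, and those who had also left the study would not be interviewed. The range assumes sampling from the whole arm of 77.

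No primary outcome or hypothesis test is affected. The point bears on items (ix) and (x) of the secondary objective and on exploratory questions 5 and 6. It is worth making because the improvement is cheap.

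**What to change.** In Study Design and In-depth Interviews:

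- Draw the 30 at random from all mothers allocated to EXAT, and state when the draw is made. Doing it at allocation is cleanest.
- Keep each selected mother in the sample whatever her attendance.
- Offer the first interview at T1 or, if a mother is leaving the study and agrees, when she stops. Reword the programme-completion phrase to match.
- Add one question to Appendix D on reasons for stopping or missing sessions.
- State how replacements are chosen, and report how many selected mothers stopped, were interviewed, declined or were replaced.

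While editing, align the label of the six-month interview: Sample Size calls it T2, whereas Study Design and In-depth Interviews call it T3.

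The target stays at 30 and no extra staff are needed. The cost is some refusals, a few short interviews, interviews at less predictable times, and possibly a few replacements to reach the 25 given for saturation. This version is dated April 2024 in a study scheduled for 2022 to 2024, so a draw at allocation may no longer be possible for mothers already enrolled. For them, the report of numbers selected, stopped, interviewed and declined should still be feasible.

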Appendix A: CONSORT diagram for the proposed study

Appendix B: Conceptual Framework of the proposed study

Appendix C: Sessions Outline & Structure of an EXAT Dyadic Group Session

Themes of the Dyadic Expressive Arts-based Intervention Program

Session 1	Communication: interaction with or without words
Session 2	Relationship: happy moment and joyful relationship
Session 3	Expression: playfulness and de-stress expression
Session 4	Empathy: understanding and empathy through arts

Session 5 Interaction: creative interaction
Session 6 Care: love and concern

Session 7 Gratitude: appreciation and gratitude Session 8 Connection: collaboration and connection

A Typical Session (1.5 hour)

	Process	Purposes
Greetings and check-in	 Use verbal or non-verbal means i.e. gestures, voice, images etc. to greet and try to present how they are at the moment Briefly introduce the theme of the session verbally Offer a brief recap of previous session starting from the 2nd session 	 Transit from the real world to the therapeutic space. Establish rapport and relationship Have an idea of the focus of the session Build connection with previous session(s)
Warm Up	Use musical rhythm or simple movement sequence to interaction with each other within the dyad and the group Introduce the theme for art creation using music and movement	Warm-up physically and psychologically Prepare for the art creation and interactions
Arts creation and response	Use different art forms to create artworks together or individually, based on different themes of the session (see above) Share the artworks with each other and the group Appreciate and response to each other's artworks through verbal/nonverbal means Therapist will facilitate further sharing and discussion, and help participants to consolidate and summarize the experience/discovery from the process	Facilitate creative expression and interaction between mother and child, and also among the group members Foster mutual support and relationship in the group Share the experiences with and learn from other dyads in the group Consolidate the experiences and create articulation to foster positive mother-child relationship
Closure	Create a dyadic gesture or sound, with or without verbal language, to say thank you and goodbye to the group	Closing the session Transit to the real world

Appendix D: Interview Guide for Qualitative Interview

Questions	Potential probes
What was your experience like about the 8-week Dyadic Expressive Arts-based Group Intervention?	Acceptability of the program Satisfaction towards the program
2. What changes you have observed in your relationship with the children when compared with the times before you joined the program?	Mother-child relationship
3. What changes you have observed in your caregiving experience when compared with the times before you joined the program?	Perception of caregiver's role, caregiver stress, and caregiver burden
4. What changes you have observed in your mood and general feelings when compared with the times before you joined the program?	n Mother's psychological wellness
5. What changes you have observed in your child's behaviours when compared with the times before you joined the program?	Children's emotional expressions, every day behavioural patterns
6. What are the other changes you have observed in you or in your child when compared with the times before you joined the program?	Family relationships with significant others; caregivers' own social/ occupational life
7. You have mentioned that you have observed changes in (i) your relationshi with the children, (ii) caregiving experience, (iii) mood & general feelings, and (iv) your child's behaviours. What are the possible reasons for these observed changes in these domains? OR You have mentioned that there are no changes in (i) your relationship with the children, (ii) caregiving experience, (iii) mood & general feelings, and (iv) your child's behaviours. What are the possible reasons for the lack of change in these areas?	attributable to the changes.
8. What kind of learning you can bring forward into your real-life situations, or in your caregiving experience?	How the mothers apply and generalize the learning from the classroom setting into real life situations.

References

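### The sample interview guide presumes change in five of its eight questions, and no legible question or probe asks about worsening or unhelpful experiences, so the qualitative themes may lean towards reported change

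*Combined protocol and SAP*

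**What the plan says.** Appendix D of the combined protocol and SAP lists eight interview questions with suggested probes.

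- Question 1 is an open question: "What was your experience like about the 8-week Dyadic Expressive Arts-based Group Intervention". One of its probes is "Acceptability of the program"; the other is satisfaction.
- Questions 2 to 5 share the stem "What changes you have observed in" and apply it in turn to the relationship with the child, the caregiving experience, the mother's mood and the child's behaviour. Question 2 in full is "What changes you have observed in your relationship with the children when compared with the times before you joined the program".
- Question 6 asks about other changes "you have observed in you or in your child when compared with the times before you joined the program".
- Question 7 has two alternatives. One asks for the reasons behind the changes reported. The other begins "You have mentioned that there are no changes in (i) your relationship with the children", continues through the same four domains and asks why nothing changed.
- Question 8 asks "What kind of learning you can bring forward into your real-life situations, or in your caregiving experience".

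Under Exploratory Questions, item 6 sets out what the qualitative work is to explore: "The potential factors and conditions that may affect how and why the EXAT intervention works or does not work for the participating dyads", together with mothers' perceptions, acceptability and everyday use of the skills. Study Design draws the 30 interviewees from the intervention arm, with interviews at T1 and T3. In-depth Interviews describes Appendix D as a sample guide. Data Analysis, item 3, combines the interview themes with the arts-based and quantitative results when judging how effective the intervention was.

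**The concern.** A question that asks what changes someone saw takes it as given that there were some. A mother who noticed nothing has to contradict the interviewer in order to say so, and here she would have to do it up to five times before question 7 acknowledges her position. A mother whose child became harder to manage, or who found the sessions a strain, is never asked about it directly.

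Two features of the plan make this matter. First, the themes are not only descriptive: they are to be read together with the trial data in evaluating effectiveness. Second, exploratory question 6 is two-sided. Explaining why the intervention does not work for some dyads needs accounts from dyads who did not respond or got worse, and the guide does little to draw those out. Because all interviewees received the intervention, there is also no parallel set of control-arm interviews against which to set the amount of perceived change.

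**Working it through.** No sample size, power or error rate is involved. The check is a classification of the eight printed questions, followed by a look at what question 7 can accommodate.

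**Count by wording (Appendix D)**

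| Question | Topic | Presumption in the wording | Explicit room for no change | Explicit room for worsening or unhelpful effects |
|---|---|---|---|---|
| 1 | Overall experience | None (open) | No | No |
| 2 | Relationship | Change | No | No |
| 3 | Caregiving | Change | No | No |
| 4 | Mood | Change | No | No |
| 5 | Child's behaviour | Change | No | No |
| 6 | Anything else | Change | No | No |
| 7 | Reasons | Depends on the branch | Yes, second branch | No |
| 8 | Learning | Learning | No | No |

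- Presume change: questions 2 to 6, so 5 of 8.
- Presume change or learning: 5 + 1 = 6 of 8.
- Open stem with no presumption: 1 of 8 (question 1).
- Explicitly allow for no change: 1 of 8 (question 7, second branch).
- Explicitly ask about worsening or unhelpful effects: 0 of 8.

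**What question 7 covers as printed**

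Each branch lists the same four domains together: one for change, the other for no change. If each domain is simply changed or unchanged, there are 2^4 = 16 possible patterns. The printed wording fits two of them (all four changed, none changed) and leaves 16 − 2 = 14 mixed patterns without a matching branch. These patterns are not equally likely, so 14 of 16 describes the wording and does not estimate how many mothers are affected. The change branch also does not separate improvement from deterioration. A mother who reports a better relationship, unchanged mood and worse child behaviour fits neither branch.

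**Set against the plan's own question**

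Exploratory question 6 needs material on success and on failure. For success, questions 2 to 6, the first branch of question 7 and question 8 all supply prompts. For failure, the direct prompt is the second branch of question 7, with question 1 giving a general opening. For harm or burden arising from the programme itself, there is no legible prompt.

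**The case against.** A reader might infer that the interviews cannot fairly settle whether the intervention works. The documents do not support that, for these reasons.

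- **The qualitative question is a different one.** Exploratory question 6 concerns how and why the intervention works or does not. Whether it works is the subject of Hypotheses 1 to 3, which are tested in the randomized comparison with two-sided mixed-effects models. Study Design gives the interviews the role of helping to interpret those results.
- **Non-response is not shut out.** Question 1 comes first, is neutral, and has acceptability and satisfaction probes that can be answered negatively. The second branch of question 7 asks directly why nothing changed.
- **Change has no stated direction.** Questions 2 to 6 presume change, not benefit, so a pull specifically towards benefit is an inference. The probes for question 3 also name stress and burden, although in relation to caregiving and not to the programme.
- **The guide is a sample.** The interviews are in-depth and conducted by team members familiar with the method, who may ask about domains separately or use both branches.
- **One probe cannot be read.** The probe beside question 7 is cut off in the text, so nothing missing there can be held against the plan.
- **Worsening can be detected elsewhere.** The maternal scales and the teacher or social worker checklist can show group-level deterioration.

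All of this stands and limits the point. It does not remove it. Appendix D is the only interview guide in the plan, and one open question does not offset five stems that presume change. Scale scores do not replace a mother's own account of what was unhelpful. The themes still enter the overall judgement of effectiveness.

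Mothers necessarily know which programme they attended, and the interviewers belong to the research team. Neither is counted here as a separate defect, and rewording the guide would not alter either.

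**Conclusion.** The point holds as a minor, inexpensive improvement to the interview guide. Questions 2 to 6 presume change, question 8 presumes learning, question 7 as worded has no place for a mixed picture, and no legible question or probe asks about worsening or unhelpful experiences. The likely consequence is that themes lean towards reported change and give thin information on poor response, which is half of what exploratory question 6 asks about.

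In size, this is 5 of 8 questions (6 of 8 with question 8) presuming change or learning, and 0 of 8 inviting worsening. The effect on the themes cannot be computed from the documents. The conclusion assumes that interviewers stay close to the printed wording; the more freely they adapt it, the smaller the problem. It does not touch the randomized comparison, and it does not show that the interviews are unable to inform the plan's question.

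**What to change.** Four edits to Appendix D:

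1. Reword questions 2 to 6 along the lines of *What, if anything, has changed in [domain], for better or worse, or has it stayed the same?*
2. Ask question 7 one domain at a time, seeking reasons separately for areas that improved, stayed the same or worsened.
3. Open question 8 with *What, if anything,* so that having learned nothing usable is an acceptable answer.
4. Add one question: *Was anything about the group unhelpful, difficult or upsetting for you or your child?*

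Nothing changes in sample size, randomization, outcomes or the quantitative analysis. The cost is the redrafting of one appendix and slightly longer interviews.

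The real downside is timing. The document is version 5, dated April 2024, within a 2022 to 2024 study period, and the bars of the Gantt chart are not legible, so some interviews may already have been held. Those under the present wording must be flagged in the analysis. Where a mother's T1 and T3 interviews used different versions, differences between them should be read with that in mind.
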